Functional magnetic resonance imaging (fMRI) studies by our team converge on the central role of working memory in smoking relapse. We showed that brief (e.g., 24 hr.) abstinence from smoking produces working memory deficits that are associated with reduced neural activity in cognitive control circuits and weakened resting state functional connectivity [25-29]. These altered brain responses may compromise cognitive resources needed to resist urges to smoke, thereby contributing to relapse [26, 30]. While working memory is one mechanism underlying relapse, additional neurobehavioral pathways are clearly important [31]. For example, neural reactivity to smoking cues also increases risk of relapse [31, 32]. Further, psychological stress can enhance neural responses to smoking cues [33, 34] and increase smoking intensity [35, 36]. Stress can also impair working memory [37]. The proposed study, to our knowledge, will be the first prospective study to examine the contributions of resting BOLD and BOLD signal change during working memory, cue reactivity, and psychological stress to subsequent smoking relapse. We will determine whether these mechanisms contribute to relapse beyond subjective and behavioral assessments, and explore the interactions among these processes.

Using our validated fMRI abstinence challenge paradigm [25, 27-30], 200 smokers will complete two 1-hour pre-treatment fMRI scans: after smoking satiety and after 24 hours of confirmed abstinence. We will examine neural responses during performance of tasks probing working memory, cue reactivity, and stress response as well as resting state functional connectivity. Participants will then set a target quit date, receive smoking cessation counseling, and be monitored for 6 months to assess time (days) to relapse, using a validated smoking relapse protocol [30, 38]. The primary outcome is time to relapse. Secondary outcomes include abstinence symptoms and smoking status at 30 days.

OBJECTIVES

1. Overall Objectives - (Main Study)

Aim 1: To identify brain mechanisms that increase vulnerability to relapse, using a pre-treatment abstinence challenge paradigm.

Hypothesis: *Altered Blood Oxygen Level Dependent (BOLD) signal during 24-hr abstinence challenge (vs. smoking satiety) will increase the risk of faster relapse during a subsequent quit attempt.*

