The proposed study is a prospective observational neuroimaging investigation utilizing a pre-treatment abstinence challenge and fMRI assessment to elucidate the mechanisms underlying smoking relapse. As shown in **Figure 1**, 200 eligible consenting smokers will be scanned on two separate occasions prior to the scheduled target quit date (week 4): once during smoking satiety and once after 24 hours of biochemically confirmed abstinence (order counterbalanced). The pre-treatment scans will both include a resting BOLD MRI scan and a BOLD fMRI scan while performing validated tasks probing working memory, cue reactivity, and stress reactivity. Participants will have an individual pre-quit counseling session (week 3), and will be counseled and monitored (with biochemical confirmation) for 6 months post target quit date, with the addition of a 12 month Follow-up survey completed remotely.

Recruitment & Retention Pilot

This pilot study will utilize a randomized controlled trial design to evaluate two components of behavioral economic strategies to improve recruitment and retention. To be eligible for the pilot study participants must meet all eligibility criteria for one of the four participating studies (828958, **824061**, 824860, 828125), have a phone capable of receiving SMS messages, and consent to receive SMS messages. ~576 participants will be enrolled across the four

[figure not shown]

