Pre-Quit Counseling (~week 3). Participants will schedule their pre-quit session after completing the second MRI scanning session. During this visit participants will have their carbon monoxide (CO) assessed and will complete paper and pencil questionnaires (PANAS, MNWS, QSU & TLFB) in addition to attending a 1-hour semi-structured individual (in person) smoking cessation counseling session. Training and quality assurance measures will be established to ensure optimal delivery of the smoking cessation protocol. We will review audiotapes of sessions for the first 2 months of the trial and randomly throughout the trial to ensure protocol adherence and to prevent intervention drift. Counselor adherence to the treatment protocol will also be facilitated by use of highly structured protocols. The counseling session begins with a discussion of reasons for quitting, the model of smoking as a learned habit, triggers for smoking, and trigger management. Participants will receive brief training in how to manage withdrawal symptoms and relapse prevention counseling (e.g., identifying high risk situations or triggers to smoke, being prepared for and coping with high risk situations, limiting access to cigarettes, managing a slip and preventing a relapse, developing a personal relapse prevention plan, and managing a complete relapse). Smokers will also receive the NCI Clearing the Air self-help smoking cessation booklet. Counseling sessions may be recorded (audio) to ensure every participant is receiving the same standard of counseling. Participants will be informed if a counseling session is being recorded. The recording will be deleted after it is reviewed.

Monitoring Visits During 30-Day Abstinence Period (~Weeks 4-8). Beginning with the target quit date (TQD) (week 4) and weekly thereafter (weeks 5, 6, 7, 8), participants will attend a brief center visits. During the first week following TQD there will be two monitoring visits to closely monitor abstinence. These visits can be scheduled any time between 8am and 7pm. The entire session will last about 45 minutes.

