The target quit date session will be scheduled to occur up to 2 weeks following the pre-quit session. Prior to the booster counseling sessions, self-reported smoking will be assessed (time line follow back, CO, saliva cotinine and urinary cotinine); we will also administer self-report questionnaires (e.g., smoking urges, withdrawal and mood). Days to relapse (primary outcome) will be defined as number of consecutive days prior to 7-day relapse (7 consecutive days of smoking). Participants will then meet with a smoking cessation counselor for a 15 minute booster counseling session. Participants will receive small monetary incentives for each week of biochemically confirmed abstinence based on CO level (<=5ppm) and/or urine cotinine assessment (NicAlert, Nymox Pharmaceutical Corporation, Hasbrouck Heights, NJ) that also indicates no smoking during the past 7 days (\$75/week). Participants will be paid in cash after abstinence has been verified (and will not be paid for a missed visit). There is a \$50 bonus for participants who have attended at least 4 of the 5 in-person monitoring visits. Telephone assessments and counseling may be provided if participants miss a visit, at the discretion of the PI.

6 Month Follow-up (~Week 28). Participants who are biochemically verified to be quit at MV5 will be contacted 24 weeks post TQD by telephone to complete a brief survey of their smoking practices using the timeline follow-back assessment. Those who report not smoking a cigarette for at least the past 7 days prior to completing the survey will be asked to come to the Center for biochemical verification of smoking status by providing CO, saliva cotinine and a urine cotinine sample.

12 Month Follow-up (~Week 52). Participants who completed all visits up to and including the Pre-Quit visit will be contacted 48 weeks post TQD by telephone to complete a brief survey of their smoking practices and eating behavior. All measures collected at the 6 Month Follow-up will be collected with the addition two questions about readiness and intention to quit smoking (if applicable).

Table 2. Measures and Time Points

Activity	Phone Screen	Intake	fMRI Scans	Pre-Quit	TQD	MV 1-5	Follow-up	12-month Follow-up
Weeks	-1	0	1, 2	3	4	5, 6, 7, 8	28	52
Demographics		X						
Urine drug screen		X	X					
Urine pregnancy screen		X	X					
ETOH history/BrAC		X						
Height		X						
Weight		X						
Smoking behavior (FTND)		X						
Medical history form		X						

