Salivary testosterone: Salivary testosterone will be used to control for between-session differences that may occur due to change in testosterone levels in male and female participants. Testosterone (pg/ml) will be collected at the start of the scan session. Approximately 2 ml of saliva will be collected using a passive drool method and saliva collection aid (Salivette LLC, State College, PA, USA). The saliva will be stored in plastic vials at –20°C. Saliva samples will be assayed using testosterone EIA kits (Salimetrics LLC, State Collect, PA, USA). Salivary testosterone is highly correlated with plasma testosterone [55].

fMRI Measures: See fMRI Scanning Sessions above.

Primary Outcomes (Main Study): Multiple measures of abstinence will be measured for this study. The primary outcome will be the number of days to relapse following the target quit date. Relapse will be confirmed using a conventional SRNT guideline criterion of either a positive biochemical verification of smoking [3, 56] or 7 consecutive days of smoking based on self-report (it is very unlikely that a subject would meet the latter criterion without also meeting the former, given the long half-life of cotinine). The days to relapse will be based upon time from target quit date to the first day of the relapse period. Self-reported daily smoking data will be collected using a validated timeline follow-back method [57]. Self-reported abstinence will be biochemically verified on a weekly basis using urine cotinine (<100ng/ml) [56] and a CO reading

of ≤5PPM. Drop-outs will be considered relapsers following the last date of abstinence data provided [7, 58]. Secondary outcomes will include days to first “slip”, and cross-sectional measures of 7-day and 30-day point prevalence (biochemically verified weekly with cotinine, which provides an assessment of smoking in the last 7 days).

Carbon Monoxide (CO): The CO monitor is a handheld device that uses a disposable mouthpiece, reports CO in parts per million (ppm), and takes about 5 minutes to administer. Carbon monoxide measurements will be collected from smokers at each visit as a biochemical verification of smoking exposure.

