Urine Cotinine: Smoking status will be assessed with NicAlert™ urine dipsticks from Nymox Pharmaceutical Corporation. A midstream urine sample of approximately 25mL will be used to test for the presence of cotinine. Results will appear in one of seven category levels of usage. Level 0 indicates no detectable tobacco use; levels 1-2 indicate presence of cotinine, but as a non-user, and levels 3-6 indicate cotinine consistent with tobacco use. Participants with results in levels 3-6 will be considered smokers. Urine cotinine will be assessed at all Monitoring Visits 2-5, if participant has reported weekly abstinence.

Saliva Cotinine: Saliva cotinine will be collected to biochemically verify smoking status. Saliva samples will be collected at monitoring visits 2-5 from participants who report smoking abstinence and have a CO value of less than or equal to 5ppm.

Primary Outcomes (Recruitment & Retention Pilot Study):

Meeting Eligibility Criteria: The primary outcome is the percentage of subjects who meet final eligibility criteria (i.e., enrollment). We chose this as the outcome based on our data suggesting that subjects who meet these criteria are highly likely to reach ITT status.

Secondary Subjective Outcomes (Main Study):

Mood: Positive and Negative Affect: The Positive and Negative Affect Schedule (PANAS) [59], a 20-item Likert-format self-report measure, will be used to assess Positive Affect (PA; 10 items, e.g., enthusiastic, strong) and Negative Affect (NA; 10 items, e.g., distressed, upset), two dominant and generally orthogonal dimensions of affect.

Nicotine Withdrawal: The Revised Minnesota Nicotine Withdrawal Scale (MNWS-R) [60] is a fifteen-item self-report measure where participants rate their feelings of withdrawal on a scale of 0 (none) to 4 (severe). This measure will be administered at all study visits.

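### The 24-week contact is limited to participants verified quit at about day 28, so those neither relapsed nor verified have no scheduled assessment in the rest of the 168-day primary window and no stated outcome rule

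*Combined protocol and SAP*

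**What the plan says.** All places are in the combined protocol and SAP.

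- **Background – Main Study:** participants will "be monitored for 6 months to assess time (days) to relapse". The Design section says they "will be counseled and monitored (with biochemical confirmation) for 6 months post target quit date". Neither passage limits this to a subgroup, and Table 2 lists timeline follow-back (TLFB), CO and cotinine at week 28 without restriction.
- **Procedures, Monitoring Visits:** starting with the target quit date (TQD, week 4) and "weekly thereafter (weeks 5, 6, 7, 8), participants will attend a brief center visits". Table 3 places MV4 in week 7 and MV5 in week 8.
- **Procedures, 6 Month Follow-up:** "Participants who are biochemically verified to be quit at MV5 will be contacted 24 weeks post TQD by telephone". No contact is scheduled between MV5 and that call.
- **Relapse, Procedures:** days to relapse is the "number of consecutive days prior to 7-day relapse (7 consecutive days of smoking").
- **Relapse, Primary Outcomes (Main Study):** either a positive biochemical test or 7 consecutive self-reported smoking days. Days to first slip is a separate secondary outcome. The section adds: "Drop-outs will be considered relapsers following the last date of abstinence data provided".
- **Measures, Urine Cotinine:** "Urine cotinine will be assessed at all Monitoring Visits 2-5, if participant has reported weekly abstinence". Saliva cotinine further requires CO of 5 ppm or less.
- **Procedures, 12 Month Follow-up:** "Participants who completed all visits up to and including the Pre-Quit visit will be contacted 48 weeks post TQD by telephone". Table 2 marks TLFB there, but neither CO nor cotinine.
- **Statistical Analysis, Aim 1:** Cox regression on a censored time to event. No censoring rule is given for participants who are neither relapsed nor verified.

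**The concern.** Whether a participant is observed for the remainder of the primary window depends on attendance and smoking status at one visit early in that window. Two kinds of participant can fail the condition without having relapsed.

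1. Someone who admits a slip in the week before MV5, short of 7 consecutive smoking days, with CO of 5 ppm or less. Under the Measures section this person gets no cotinine test, so cotinine cannot verify them as quit, and neither relapse criterion is met.
2. Someone who misses MV5. The plan foresees missed visits: its completion bonus requires only 4 of 5, and a telephone assessment is at the PI's discretion. A telephone call cannot verify abstinence biochemically.

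The analyst must then end these people's time at about day 21 to 28 as censored, or count them as relapsed under the drop-out rule. Censoring gives up later events among people who may have just lapsed. Counting them as relapsed gives wrong dates to some and false events to others. Relapse data for days 29 to 168 that are never collected cannot be recovered by analysis.

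**Working it through.** **Timing.**
- MV5: (8 − 4) × 7 = day 28. MV4: (7 − 4) × 7 = day 21.
- 24-week contact: 24 × 7 = day 168. 48-week contact: 48 × 7 = day 336.
- Unobserved after MV5: 168 − 28 = 140 days, 140/168 = 83% of the window.
- Unobserved if MV5 is missed and MV4 is the last contact: 168 − 21 = 147 days, 147/168 = 87.5%.

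**The plan's own power figure.** Inputs from Power and Sample Size Considerations: n = 200, alpha 0.0085, one-sample effect size 0.25, HR 1.32, power 80%. Sidedness is not stated.
- One-sample test, two-sided: power = Φ(0.25 × √200 − 2.632) = 0.817 by normal approximation and 0.809 by noncentral t. The stated 80% reproduces. One-sided it would be 0.875 and 0.869.
- Cox model, HR per 1 SD: events = (z for alpha/2 + z for power)² / (ln HR)² = (2.632 + 0.842)² / (ln 1.32)² = 156.5, so about 157 events, or 78% of 200. The plan does not state this event rate, but its HR of 1.32 requires it.

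**Power by number of events.** Power = Φ(√events × ln 1.32 − 2.632):

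| Events | Power |
|---|---|
| 157 | 80% |
| 140 | 74% |
| 120 | 66% |

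**Illustrative size.** The documents give neither the share of participants who are unrelapsed but unverified at MV5 nor their later relapse rate. Assume 5–20% of 200 (10 to 40 people), of whom 30–70% relapse by day 168, against 157 events in total.
- If censored near day 28, events lost = 200 × share × relapse rate. Lowest: 200 × 0.05 × 0.30 = 3, power 79%. Highest: 200 × 0.20 × 0.70 = 28, leaving 129 events, power 70%.
- If counted as relapsed, false events = 200 × share × (1 − relapse rate). Lowest: 200 × 0.05 × 0.30 = 3. Highest: 200 × 0.20 × 0.70 = 28.

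**Effect on the hazard ratio.** This was simulated with n = 200, Weibull relapse times with 55% relapsed by day 28 and 78% by day 168, true HR 1.32 per SD, and 400 replicates. Of those event-free at MV5, 15–50% fail the condition (about 13 to 44 people), more often those who later relapse. All these rates are assumptions.

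| Handling | Mean HR | Mean events |
|---|---|---|
| Full follow-up | 1.32–1.33 | 155 |
| Censored at day 28 | 1.32–1.33 | 145 to 122 |
| Counted as relapsed at day 28 | 1.31 to 1.26 | 158 to 166 |

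Under these assumptions censoring costs events but leaves the HR unchanged. Imputing relapse attenuates it slightly, reaching 1.26 only if half of those event-free at MV5 fail the condition.

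**The case against.** A reader might infer that everyone who slips leaves follow-up at day 28, and that the primary hazard ratio is therefore biased. The documents do not support that.

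- A participant who slipped earlier but is verified quit at MV5 stays in follow-up.
- CO is taken at every visit, and under Primary Outcomes a positive biochemical test is itself relapse. A slip with CO above 5 ppm at MV5 is then already an event and nothing is lost. The group is larger only under the Procedures definition.
- The Monitoring Visits text lists saliva and urine cotinine before booster sessions without requiring reported abstinence. On that reading, some who admit a slip would be tested.
- Those who miss MV5 may fall under the drop-out rule or be reached by telephone.
- All Pre-Quit completers are due a call at 48 weeks with TLFB, and relapse can be established from self-report alone.
- Under censoring, the simulation shows no HR bias, and every group size is assumed.
- Version 19 is dated April 2020 and enrollment runs from June 2016 to January 2021, so a changed contact rule would reach mainly late enrollees.

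These points narrow the group and remove any claim of demonstrated bias. They do not close the gap. The drop-out rule does not say whether one missed visit, or not being called by design, makes someone a drop-out. The 48-week survey falls 168 days after the window ends, is remote and unverified, depends on electronic re-consent (Confidentiality section), and has no stated look-back or role in dating relapse. The conflict with 6-month monitoring remains.

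**Conclusion.** The point holds in limited form. The 24-week contact condition conflicts with the stated 6-month monitoring for time to relapse. It leaves unrelapsed, unverified participants without a scheduled assessment for 140 to 147 of 168 days, and the plan does not say whether they are censored or counted as relapsed. That much follows from the documents alone.

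The consequence is probably modest: a loss of 3 to 28 events and power of 79% to 70% instead of 80% if they are censored, or mis-dated and some false events if relapse is imputed. Those figures rest on the assumed 5–20% share, the assumed 30–70% later relapse, and the 157 events implied by HR 1.32 at two-sided alpha 0.0085. This is a worthwhile, inexpensive improvement to ascertainment of the primary outcome, not evidence that the Aim 1 analysis fails.

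**What to change.** 1. Reconcile the relapse definitions in the Procedures and Primary Outcomes sections. The next step cannot be applied consistently until this is done.
2. Offer the existing 24-week TLFB call, and the verification visit for those reporting abstinence, to every Pre-Quit completer who has not met the reconciled definition by MV5, including those who slipped or missed MV5.
3. For those not reached, or already past week 28, use the 48-week TLFB with a stated look-back to the TQD to date relapse before the drop-out rule is applied.
4. State one rule for anyone still unobserved: censor at the last abstinence data with relapse imputation as a sensitivity analysis, or the reverse. Say whether a single missed visit makes a drop-out.

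**Cost.** From Table 3, each added call takes about 15 minutes and pays $35; a verification visit adds $35 plus $10 travel. For the assumed 10 to 40 people, calls cost $350 to $1,400, and verification at most $450 to $1,800 more if all attend and take the flat travel payment. A TLFB back to the TQD from week 48 means longer, less reliable recall. Earlier and later enrollees would have different follow-up schedules, which should be reported. About 46 of 56 enrollment months had passed by Version 19. With even accrual (an assumption), roughly (46 − 6.4)/56 = 71% of enrollees were already past week 28 (28 weeks is about 6.4 months), so steps 3 and 4 matter most for them.
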